11.8.2. Vital Signs for Pregnant Women

Vital Sign Parameter (Absolute)	Units	Clinical Concern Range	
		Lower	Upper
Systolic Blood Pressure	mmHg	< 85	> 160
Diastolic Blood Pressure	mmHg	< 45	> 100
Heart Rate	bpm	< 40	> 110

11.8.3. Fetal Heart Rate

Parameter (Absolute)	Units	Clinical Concern Range	
		Lower	Upper
Heart Rate	bpm	< 110	> 160

11.9. Appendix 9: Model Checking and Diagnostics for Statistical Analyses

Endpoint(s)	
 • Time to delivery • Length of hospital stay
Analysis	
 • Finite Mixture Models for the Time to Delivery • Analysis of Covariance for the Length of hospital stay
	
 • For the time to delivery, the FMM model assumptions will be examined and appropriate adjustments maybe applied based on the data. • Length of hospital stay will be log-transformed prior to the model fitting.

11.10. Appendix 10: Abbreviations & Trade Marks

11.10.1. Abbreviations

Abbreviation	Description
ADaM	Analysis Data Model
AE	Adverse Event
AESI	Adverse Event of Special Interest
AFI	Amniotic Fluid Index
ALP	Alkaline phosphatase
ALT	Alanine aminotransferase (SGPT)
AST	Aspartate aminotransferase (SGOT)
BMI	Body mass index
BPM	Beat Per Minute
CI	Confidence Interval
CSR	Clinical Study Report
DRE	Disease-related Event
eCRF	electronic Case Report Form
EDD	Estimated Date of Delivery
EM	Expectation-maximization
EP	Established Progesterone Use
EPDS	Edinburgh Postnatal Depression Scale
EQ-5D-5L	EuroQol 5-dimensional 5-level
fFN	fetal Fibronectin
FMM	Finite Mixture Models
GA	Gestational Age
GSK	GlaxoSmithKline
HR	Heart rate
ICH	International Conference on Harmonization of Technical Requirements for Registration of Pharmaceuticals for Human Use
ICU	Intensive Care Unit
IDMC	Independent Data Monitoring Committee

Abbreviation	Description
IDSL	Integrated Data Standards Library
IP	Investigational Product
ITT	Intent-to-treat
Kg	Kilogram
MedDRA	Medical Dictionary for Regulatory Activities
NICU	Neonatal Intensive Care Unit
PK	Pharmacokinetic
PP	
PPROM	Preterm Premature Rupture of Membranes
RAP	Reporting and Analysis Plan
RDS	Respiratory Distress Syndrome
SAC	Statistical Analysis Complete
SAE	Serious Adverse Event
SAS	Statistical Analysis Software
SI	System Independent
SD	Standard deviation
SDTM	Study Data Tabulation Model
SOP	Standard Operating Procedure
TRT	Treatment
ULN	Upper limit of normal

11.10.2. Trademarks

Trademarks of the GlaxoSmithKline Group of Companies	Trademarks not owned by the GlaxoSmithKline Group of Companies
NONE	NONMEM
	SAS
	WinNonlin

11.11. Appendix 11: List of Data Displays

A separate document for shells contains all table, listing and figures' (TLFs) for the planned final analysis. However, due to early termination of the study, only TLFs listed in this appendix will be generated.

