8.3.5.2. Safety Analyses

No formal hypothesis statistical test will be performed for the safety data. All safety analyses will be done using the safety population, unless otherwise specified. The objective of the safety analysis is to describe the maternal, fetal, and neonatal safety profile during/after IV retosiban treatment as compared with atosiban treatment. As such, maternal, fetal, and neonatal safety data will be summarized by treatment group.

All summary statistics of continuous variables will include: n, mean, median, standard deviation, minimum, and maximum. For binary outcomes, all summary tables will include the number and percentage of subjects with the response/event. All summary tables will include N for each group (i.e., the total number of subjects randomly assigned to each group within the appropriate population).

To further describe the maternal, fetal, and neonatal safety profile of retosiban, the following subgroups may be explored:

- GA of pregnancy at randomization
- Established progesterone use
- GA at delivery
- Maternal age
- Region/site

For each subgroup, maternal, fetal, and neonate safety data will be summarized by treatment and subgroup, as described above.

8.3.5.2.1. *Extent of Exposure (Maternal)*

The total volume administered during the infusion and the total volume administered overall will be summarized. If applicable, the number of infusion interruptions and the time taken for each infusion will be summarized. The frequency and percentage of women who discontinued study treatment and reason for discontinuation and who increased study treatment from 6 to 12 mg will be summarized.

8.3.5.2.2. *Adverse Events*

Adverse events will be coded using the MedDRA dictionary and grouped by body system. Adverse events will be summarized by treatment group. Within each group, AEs will be summarized by frequency and proportion of total subjects, by event type, and by category of body system. Separate summaries will be given for all AEs, drug-related AEs, SAEs, and AEs leading to discontinuation. Where appropriate, each phase of the study (pretreatment, treatment, and follow-up) will be tabulated separately.

The proportion of subjects reporting at least 1 AE, 1 IP-related AE, 1 SAE, and 1 AE leading to discontinuation will also be calculated for each group.

Adverse events of special interest (see Section 6.3.2.3) and DREs (see Section 6.3.7) will be similarly summarized.

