8.2.3.1. All Adverse Events

The number and percentage of subjects reporting at least one AE for each SOC and PT will be reported by treatment group. The summary will include both non-serious and serious AEs. A listing of all adverse events will be provided. Also, the above summary will be produced by subgroups defined in Section **Error! Reference source not found.**

The AE will be summarized by maternal, fetal and neonatal events, separately. Also, the maternal AE by treatment phase (on-treatment, post-treatment) defined in Section 11.3.3 will be summarized.

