8.2.3.4. Serious Adverse Events

The seriousness of an AE should be assessed by the Investigator independently from the severity of the AE. A serious AE (SAE) is defined as any untoward medical occurrence that at any dose results in death, is life-threatening, requires hospitalization or prolongation of existing hospitalization, results in disability/incapacity, is a congenital anomaly/birth defect, or is possible of drug-induced liver injury with hyperbilirubinemia.

Important medical events that may not result in death, be life-threatening, or require hospitalization may be considered SAEs when, based upon medical judgment, they may jeopardize the subject and may require medical or surgical intervention to prevent one of the outcomes listed above.

SAEs will be reported in the similar manner as all AEs. A listing of SAEs will be provided. Also, the above summary will be produced by subgroups as defined in Section **Error! Reference source not found.**

The SAEs will be summarized by maternal, fetal and neonatal events, separately. Also, the maternal SAEs by treatment phase (on-treatment, post-treatment) defined in Section 11.3.3 will be summarized.

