11.3.3. Treatment States for AE Data

Non-retreated subjects

Treatment State	Definition
AE = Pre-treatment	AE Start Date < Study Treatment Start Date
AE = On-treatment	If AE onset date is on or after the treatment start date and on or before the treatment stop date. Study Treatment Start Date \leq AE Start Date \leq Study Treatment Stop Date + 1
AE = Post-treatment	If AE onset date is after the treatment stop date. AE Start Date > Study Treatment Stop Date + 1
AE Onset Time Since 1 st Dose (Days)	If Study Treatment Start Date > AE Onset Date : = AE Onset Date – Study Treatment Start Date If Treatment Start Date \leq AE Onset Date : = AE Onset Date – Study Treatment Start Date + 1 Missing otherwise
AE Duration (Days)	AE Resolution Date – AE Onset Date + 1
AE = Drug-related	If relationship is marked 'YES' on [Inform/CRF OR value is missing.

NOTES:

- If the study treatment stop date is missing then the AE will be considered to be On-Treatment if there are no post-infusion assessments and delivery.

Retreated subjects

Treatment State	Definition
AE = Pre-treatment	AE Start Date < Initial Study Treatment Start Date
AE = On-treatment	If AE onset date is on or after the treatment start date and on or before the treatment stop date. Initial Study Treatment Start Date \leq AE Start Date \leq Initial Study Treatment Stop Date + 1 or Retreated Study Treatment Start Date \leq AE Start Date \leq Retreated Study Treatment Stop Date + 1
AE = Post-treatment	If AE onset date is after the treatment stop date. Initial Study Treatment Stop Date + 1 < AE Start Date < Retreated Study Treatment Start Date or AE Start Date > Retreated Study Treatment Stop Date + 1
AE Onset Time Since 1 st Dose (Days)	If Initial Study Treatment Start Date > AE Onset Date : = AE Onset Date – Initial Study Treatment Start Date If Initial Study Treatment Start Date \leq AE Onset Date : = AE Onset Date – Initial Study Treatment Start Date + 1 Missing otherwise

Treatment State	Definition
AE Duration (Days)	AE Resolution Date – AE Onset Date + 1
AE = Drug-related	If relationship is marked 'YES' on [lInform/CRF OR value is missing.

NOTES:

- If the study treatment stop date is missing then the AE will be considered to be On-Treatment if there are no post-infusion assessments and delivery.

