11.11.5. Safety Tables

Safety Tables					
No.	Population	IDSL / TST ID / Example Shell	Title	Programming Notes	Deliverable [Priority]
Exposure					
3.01	Maternal Safety		Summary of Extent of Study Drug Exposure		
3.02	Maternal Safety		Summary of Inadequate Therapeutic Response		
Maternal Adverse Events					
3.11	Maternal Safety		Summary of Maternal Adverse Events		
3.31	Maternal Safety		Summary of Maternal Adverse Events by Maximum Grade or Intensity		
3.41	Maternal Safety		Summary of Most Common Maternal Adverse Events		
3.51	Maternal Safety		Summary of Maternal Serious Adverse Events		
3.71	Maternal Safety		Summary of Maternal Adverse Events of Special Interest		
3.72	Maternal Safety		Summary of Maternal Adverse Events of Special Interest by Gestational Age Group		

CONFIDENTIAL

GSK200721

Safety Tables					
No.	Population	IDSL / TST ID / Example Shell	Title	Programming Notes	Deliverable [Priority]
3.81	Maternal Safety		Summary of Maternal Disease-Related Adverse Events		
Fetal Adverse Events					
3.111	Maternal Safety		Summary of Fetal Adverse Events		
3.131	Maternal Safety		Summary of Fetal Adverse by Maximum Grade or Intensity		
3.141	Maternal Safety		Summary of Most Common Fetal Adverse Events		
3.151	Maternal Safety		Summary of Fetal Serious Adverse Events		
3.171	Maternal Safety		Summary of Fetal Adverse Events of Special Interest		
3.172	Maternal Safety		Summary of Fetal Adverse Events of Special Interest by Gestational Age Group		
Neonatal Adverse Events					
3.211	Neonatal Safety		Summary of Neonatal Adverse Events		
3.231	Neonatal Safety		Summary of Neonatal Adverse by Maximum Grade or Intensity		

CONFIDENTIAL

GSK200721

Safety Tables					
No.	Population	IDSL / TST ID / Example Shell	Title	Programming Notes	Deliverable [Priority]
3.241	Neonatal Safety		Summary of Most Common Neonatal Adverse Events		
3.251	Neonatal Safety		Summary of Neonatal Serious Adverse Events		
3.271	Neonatal Safety		Summary of Neonatal Adverse Events of Special Interest		
3.272	Neonatal Safety		Summary of Neonatal Adverse Events of Special Interest by Gestational Age Group		
3.281	Neonatal Safety		Summary of Neonatal Disease-Related Adverse Events		
Maternal Hospital Admission					
3.301	Maternal Safety		Summary of Maternal Hospital Admission (In-patient)		
Labs					
3.401	Maternal Safety		Summary of Observed Value and Change from Baseline in Hematology by Visit		
3.402	Maternal Safety		Summary of Hematology Results Outside the Reference Ranges by Visit		

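### SAP Appendix 11 lists no table of IP-related adverse events and no title showing maternal AEs and SAEs by treatment phase, and Section 9 declares neither as dropped

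*SAP*

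**What the plan says.** - **Protocol 8.3.5.2.2** (Adverse Events): "Separate summaries will be given for all AEs, drug-related AEs, SAEs, and AEs leading to discontinuation". It also plans, arm by arm, the share of women with one or more events of each kind: "reporting at least 1 AE, 1 IP-related AE, 1 SAE, and 1 AE leading to discontinuation will also be calculated for each group". Tabulation by study phase is asked for where appropriate.
- **SAP 8.2.3.1**: "the maternal AE by treatment phase (on-treatment, post-treatment) defined in Section 11.3.3 will be summarized".
- **SAP 8.2.3.4**: "the maternal SAEs by treatment phase (on-treatment, post-treatment) defined in Section 11.3.3 will be summarized".
- **SAP 8.2.3.3**: the most-common-AE summaries cover on-treatment events above 2% incidence, separately for mother, fetus and neonate.
- **SAP 11.3.3**: defines on- and post-treatment onset for each AE and a status "AE = Drug-related". A missing relationship counts as related.
- **SAP 11.11**: "due to early termination of the study, only TLFs listed in this appendix will be generated". Table shells are kept in another document.
- **SAP 11.11.5**: the maternal AE tables are 3.11 (all AEs), 3.31 (by intensity), 3.41 (most common), 3.51 ("Summary of Maternal Serious Adverse Events"), 3.71 and 3.72 (special interest, overall and by gestational age) and 3.81 (disease-related). No title refers to relationship to IP, and no AE or SAE title refers to phase.
- **SAP 9**: lists the changes from the protocol, down to neonatal ambulatory surgery. Neither item appears.

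**The concern.** One of the secondary objectives is to describe maternal, fetal and neonatal safety both during and after a 48-hour infusion. Two ordinary ways of relating an event to the drug are its timing against the infusion and the investigator's judgment of relationship. The plan defines both and then lists no table that clearly uses them for SAEs, and none at all for relationship.

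Timing is also a question the protocol itself raises. Its risk table (1.3.1, Table 1) says uterine atony is most likely when delivery falls within 24 hours of treatment. In describing the two Phase II postpartum hemorrhages as confounded, it notes that one came more than 30 days after the drug was stopped. A single SAE table covering everything from dosing to the postpartum contact would put two such events in the same row.

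If the Appendix 11 rule is followed as written, safety output required by the protocol and the SAP body is lost with no record that this was decided.

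**Working it through.** The plan gives no figure to reproduce here. The check sets the sections side by side and then makes two short calculations.

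**1. Required against listed**

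| Item | Required in | Variable defined in | Title in 11.11.5 | Declared dropped in SAP 9 |
|---|---|---|---|---|
| Drug-related AEs by group; at least one IP-related AE | Protocol 8.3.5.2.2 | SAP 11.3.3 | None | No |
| Maternal AEs, on-/post-treatment | SAP 8.2.3.1 | SAP 11.3.3 | 3.11, no phase in title | No |
| Maternal SAEs, on-/post-treatment | SAP 8.2.3.4 | SAP 11.3.3 | 3.51, no phase in title | No |
| Most common AEs, on-treatment | SAP 8.2.3.3 | SAP 11.3.3 | 3.41, 3.141, 3.241, no phase in title | Not applicable |

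The first row is the clearest gap. The drug-related summary is absent from SAP 8.2.3 as well as from Appendix 11, so the flag in 11.3.3 has no stated tabular use. For the second and third rows the SAP body still promises the split, and only the list of displays fails to show it.

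**2. How much Table 3.41 recovers**

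Inputs: 97 women randomized 1:1 (SAP 2.3), so about 48 and 49 per arm; threshold above 2% (SAP 8.2.3.3).

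- Cut applied per arm: 1/48 = 2.08% and 1/49 = 2.04%. One subject passes. This holds for any arm below 50, since 1/n > 0.02 when n < 50, so it also holds if some randomized women were not dosed.
- Cut applied to both arms pooled: 1/97 = 1.03% fails and 2/97 = 2.06% passes. Two subjects are needed.

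On the per-arm reading, Table 3.41 would show essentially every on-treatment maternal preferred term by arm. It does not separate SAEs, has no post-treatment side and carries no causality.

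**3. How much time Tables 3.11 and 3.51 cover if they are not split**

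Inputs: on-treatment runs to stop date + 1 (SAP 11.3.3), about 3 to 4 days for a 48-hour infusion. The tables take any AE starting on or after first treatment, with no upper limit (SAP 8.2.3). Collection runs to the follow-up contact (Protocol 6.3.8), which is 6 weeks after delivery, ±2 weeks (Protocol 3.1.5).

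Share = on-treatment days / (days from dosing to delivery + days from delivery to contact).

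- Long case, assumed entry at 24 weeks 0 days and delivery at 40 weeks 0 days: 112 + 42 = 154 days. 3/154 = 1.9%; 4/154 = 2.6%. With the ±2 weeks, 140 to 168 days and 1.8% to 2.9%.
- Short case, assumed delivery on day 2: 2 + 42 = 44 days. 3/44 = 6.8%; 4/44 = 9.1%. With the ±2 weeks, 30 to 58 days and 5.2% to 13.3%.

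These are shares of calendar time. They show what the tables mix; they do not measure bias.

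**The case against.** The strongest reply is that Appendix 11 gives titles only. Several of its titles leave out splits that the SAP body requires. Table 3.424 (fetal heart rate category) is by treatment and post-treatment phase under SAP 8.2.6.2. Table 3.01 (exposure) is by initial treatment, retreatment and total under 8.2.2. The single placental table, 3.501, should also be broken down by gestational age and time to delivery under 8.2.8. Phase panels inside 3.11 and 3.51 are therefore possible. This stands: the documents show that the titles do not display the split, not that it has been removed. Against that, where Appendix 11 breaks an AE table down by gestational age it gives a separate number and title (3.71 and 3.72, 3.171 and 3.172, 3.271 and 3.272). A phase panel would also not supply the missing table by relationship.

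A second reply is that reduced output is announced in general terms in SAP 2.1, 9 and 11.11, and that the protocol asks for phase tabulation only where appropriate. This is true, but SAP 8.2.3.1 and 8.2.3.4 promise the maternal split without that qualifier, and the protocol's drug-related summary carries no qualifier.

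A reader might infer that the AE tables cannot separate drug effects from the rest of pregnancy, delivery and the puerperium. The documents do not support that. The most-common tables are on-treatment by definition. The arms are randomized and blinded, so even an all-period table keeps a valid contrast. Tables by preferred term dilute a distinct infusion reaction far less than a row counting any AE would. Investigator-judged relationship does not isolate drug effects by itself. Individual AEs and SAEs also stay in listings 41, 42, 76, 77, 82 and 83, whose columns cannot be seen here.

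**Conclusion.** The conflict is real and narrow. Appendix 11 restricts output to its own list. That list has no table of IP-related AEs, which the protocol requires by group, and no title showing the maternal AE and SAE phase split that the SAP body still promises. Section 9 declares neither omission.

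As listed, three things are missing: any by-arm count of IP-related events for mother, fetus or neonate; maternal SAEs by phase; and a post-treatment view of maternal AEs. On-treatment AEs are partly covered by Tables 3.41, 3.141 and 3.241, although their titles do not say so.

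The conclusion on the phase split assumes that the unseen shells for 3.11 and 3.51 carry no phase panel. The conclusion on IP-related events rests on no listed table naming relationship. The coverage of Table 3.41 assumes arms below 50 and a per-arm cut. The time shares assume a full 48-hour infusion without retreatment. Efficacy analyses are unaffected.

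**What to change.** In SAP 11.11.5:

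1. Add a by-arm table of IP-related AEs and IP-related SAEs, with an at-least-one row, using the 11.3.3 flag. Footnote the number of events counted as related only because causality was missing.
2. Add maternal AE and SAE tables by on- and post-treatment phase, or state explicitly that Tables 3.11 and 3.51 carry that split. The SAP promises it for maternal events only, so no fetal or neonatal version is needed.
3. Label Tables 3.41, 3.141 and 3.241 as on-treatment, in line with 8.2.3.3, and say whether the 2% cut applies per arm or pooled.

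If any of these is deliberately left out, list it in Section 9 and remove the matching sentence from 8.2.3.1 or 8.2.3.4.

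The cost is a few extra tables from variables the SAP already defines, with no new data. Counting missing causality as related will inflate the related counts slightly, which is why the footnote is needed.

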11.11.1. Data Display Numbering

The following numbering will be applied for RAP generated displays:

Section	Tables	Figures
Study Population	1.01 to 1.xx	1.01
Efficacy	2.01 to 2.xx	2.01
Safety	3.01 to 3.xx	N/A
Other Analysis		
Section	Listings	
ICH Listings		1 to 200
Other Listings		From 201

11.11.2. Study Population Tables

Study Population Tables					
No.	Population	IDSL / TST ID / Example Shell	Title	Programming Notes	Deliverable [Priority]
Subject Disposition					
1.01	All Randomized		Summary of Subject Disposition		
1.03	Maternal ITT		Summary of Significant Protocol Deviations		
Demographics					
1.11	Maternal ITT		Summary of Maternal/Fetal Demographic		
1.12	Maternal ITT		Summary of Maternal/Fetal Baseline Characteristics		
1.13	Neonatal ITT		Summary of Neonatal Birth Data		
1.15	Maternal ITT		Summary of Maternal Race and Racial Combinations		
Medical Condition & Con Meds					
1.23	Maternal ITT		Summary of Obstetrical History		
1.24	Maternal ITT		Summary of Prenatal History		
1.27	Maternal ITT		Summary of Maternal Prior Medications		
1.28	Maternal ITT		Summary of Maternal Concomitant Medications		
1.29	Maternal ITT		Summary of Maternal Obstetrical Medications		

CONFIDENTIAL

GSK200721

Study Population Tables					
No.	Population	IDSL / TST ID / Example Shell	Title	Programming Notes	Deliverable [Priority]
1.30	Maternal ITT		Summary of Maternal Magnesium Sulfate		
1.31	Maternal ITT		Summary of Maternal Antenatal Corticosteroids		

11.11.3. Efficacy Tables

Efficacy Tables					
No.	Population	IDSL / TST ID / Example Shell	Title	Programming Notes	Deliverable [Priority]
Time to Delivery					
2.01	Maternal ITT		Analysis of Time to Delivery		
2.03	Maternal ITT		Summary of Time to Delivery, Retreatment or Subsequent PTL		
2.04	Maternal ITT		Analysis of Time to Delivery Using ANCOVA		
2.51	Maternal ITT		Summary Statistics for Time to Delivery by Gestational Age Group		
2.52	Maternal ITT		Summary Statistics for Time to Delivery by Established Progesterone Group		
2.53	Maternal ITT		Summary Statistics for Time to Delivery by PTL criteria (IC#4)		
2.54	Maternal ITT		Summary Statistics for Time to Delivery by Labor Onset Status		
Neonatal Composite Endpoint					
2.101	Neonatal ITT		Proportion of Neonatal Composite Endpoint		
2.102	Neonatal ITT		Proportion of Modified Neonatal Composite Endpoint		
2.151	Neonatal ITT		Proportion of Neonatal Composite Endpoint by Gestational Age Group		

CONFIDENTIAL

GSK200721

Efficacy Tables					
No.	Population	IDSL / TST ID / Example Shell	Title	Programming Notes	Deliverable [Priority]
2.152	Neonatal ITT		Proportion of Neonatal Composite Endpoint by Established Progesterone Group		
Proportion of Births					
2.181	Maternal ITT		Proportion of Births		
2.201	Maternal ITT		Proportion of Births by Gestational Age Group		
2.202	Maternal ITT		Proportion of Births by Established Progesterone Group		
Neonatal Hospital Admission: Length of Neonatal Hospital Stay					
2.301	Neonatal ITT		Analysis of Neonatal Hospital Stay		
2.321	Neonatal ITT		Summary Statistics for Neonatal Hospital Stay by Maternal Gestational Age Group		
2.322	Neonatal ITT		Summary Statistics for Neonatal Hospital Stay by Established Progesterone Group		

11.11.4. Efficacy Figures

Efficacy Figures					
No.	Population	IDSL / TST ID / Example Shell	Title	Programming Notes	Deliverable [Priority]
Time to Delivery					
2.01	Maternal ITT		Kaplan-Meier Plot of Time to Delivery by Treatment Group		

